Our primary hypothesis is that the effect will be significantly larger in rs2832407 C-allele homozygotes than in A-allele carriers. We will also examine the SNP's moderating effects on the efficacy of topiramate in improving other self-reported drinking measures (e.g., abstinent days), adverse consequences of drinking (e.g., the Short Index of Problems score: SIP; see section 6.8.3 below), and biological measures of heavy drinking (e.g., %dCDT, an improved assay for carbohydrate deficient transferrin). Finally, we will conduct 3- and 6-month post-treatment assessments on the hypothesis that rs2832407 C-allele homozygotes will show greater reduction in primary and secondary outcomes after the medication is discontinued.

The primary outcome for the study is the frequency of heavy drinking (defined as 4 or more drinks in a day for women and five or more drinks in a day for men).

Secondary outcomes include the number of abstinent days, absence of any heavy drinking days during the last month of treatment, mean daily alcohol consumption, drinks/drinking day, %dCDT and gamma glutamyl transpeptidase (GGTP) levels, and severity of alcohol-related problems (i.e., SIP score), using models similar to those described below for the primary outcome.

2.2. Secondary Objective: To examine daily processes, including expectancies regarding the positive effects of drinking and confidence in resisting heavy drinking and their interaction with genotype and medication group to predict the intensity of nighttime drinking. We expect that evening reports of a high level of positive expectations regarding alcohol's effects and a low level of confidence in resisting heavy drinking will be associated with heavier drinking later that night.

Our secondary hypotheses are that topiramate treatment will significantly reduce both positive alcohol-outcome expectancies and confidence in resisting heavy drinking across the weeks of the study and nighttime drinking measured daily in rs2832407 C-allele homozygotes, but not A-allele carriers.

2.3 Optional MRI Sub-Study Objective: Conduct an optional sub-study to examine the effects of topiramate on resting baseline (RB) cerebral blood flow and alcohol cue reactivity using functional magnetic resonance imaging (fMRI). The goals, rationale, background and study methods for this objective are described in Appendix I: "Brain Mechanisms of Topiramate's Effects on Heavy Drinking."

3 Study Design

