3.1 General Design

This is a 12-week, prospective, randomized clinical trial of the moderating effect of rs2832407 on the efficacy of topiramate in reducing HD in 200 individuals of European descent with DSM-5

CONFIDENTIAL

This material is the property of the University of Pennsylvania. Do not disclose or use except as authorized in writing by the study sponsor

AUD. We will stratify the randomization on genotype and oversample rs2832407*C homozygotes, the most topiramate-responsive genotype, to ensure comparable numbers of subjects in the four medication x genotype groups. We will compare the efficacy of topiramate to placebo in reducing the frequency of HDDs in subjects with AUD using a two-arm, parallel-groups design. Subjects will either have a goal to reduce their drinking to safe levels or to stop drinking entirely. We will use daily data collection to examine changes in relevant process variables and their interaction with genotype and medication group as predictors of HD. This study will be registered on clinicaltrials.gov.

At each visit, all subjects will receive MM (Pettinati, Weiss et al. 2004) (see section 6.7.2), which was developed for the COMBINE Trial and which we modified to be relevant for both reducing heavy drinking and promoting abstinence. Random assignment to treatment group and double-blind conditions will be maintained throughout the study. Raters will be trained in the reliable use of all assessments. We will use serum GGTP and percent disialotransferrin (%dCDT), an improved assay for carbohydrate deficient transferrin (Helander, Wielders et al. 2010), to validate subject reports. Following a one-week pre-treatment assessment period, subjects will receive 12 weeks of treatment. There will be a 6-day taper period, during which subjects will reduce their dosage of topiramate gradually and then discontinue it completely. Daily reports during the treatment period will be obtained using interactive voice response (IVR) to identify subjective correlates of medication effects and to monitor medication use. Following the 12-week treatment period, subjects will be asked to return to the clinic for 3-month and 6-month post-treatment follow-up visits to evaluate the durability of treatment effects.

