6.3 Visit 1 (Week 1; Baseline and First Treatment Visits)

Subjects will be informed of their eligibility status within 5 days and scheduled for a baseline assessment within 30 days of the screening visit. All subjects not eligible for the study will be referred to the appropriate treatment center or other research study. Eligible subjects will undergo a **baseline** research evaluation (lasting up to 2 hours) within 30 days of completing the screening visit.

Subjects will be asked to complete a breathalyzer test. If a subject's breath alcohol concentration is $\geq 0.02\%$, an investigator will evaluate whether the subject is too impaired to complete the study assessments. The study visit may be completed at the discretion of the investigator. If the subject is deemed to be unable to complete assessments, the investigator may ask the subject to wait until his or her blood alcohol level decreases or if that is not feasible to return the next day after having consumed no alcohol. Prior to discharge from the TRC, a clinician will assess the subject to ensure that it is safe for the subject to leave. Study staff will complete the following assessments with all subjects (the exception being that only for women of childbearing potential, will study staff obtain a urine sample for a pregnancy test).

- The Patient Health Questionnaire (PHQ-9), a validated 9-item self-report measure of depressive symptoms that yields a total score of 0-27 (Kroenke, Spitzer et al. 2001), will be administered at each visit.
- The International Neuropsychiatric Interview 6.0 (Mini 6): Suicidal risk will be assessed using the MINI Suicidality section (B) at each study visit and, if rated greater or equal to 9 (i.e., clinically significant suicidal ideation), the physician will be consulted to decide on the appropriate clinical management.
- Daily Interactive Voice Response (IVR) Telephone Call (daily for 12 weeks, beginning with the initiation of treatment)

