 - Measures of treatment received: Records of medication taken will be kept and subjects will be asked to return the unused portion of study medication at each visit. The nurse will also record the number of contact hours subjects have been exposed to any alcohol treatment outside of the study.
 - The Short Index of Problems (SIP). The SIP, a 15-item instrument subset of the 50-item DrInC (Miller, 1995), measures alcohol dependence symptoms and medical, psychological,

CONFIDENTIAL

social, occupational, and legal problems. This shorter questionnaire reduces respondent burden (Feinn, Tennen et al., 2003b).

- The RAND 12-Item Health Survey (SF-12) (Ware Jr, Kosinski et al. 1996), a self-report measure of life functioning in various domains, will be completed at study baseline and endpoint. We will focus on the mental health component of the SF-12.
- Alcohol Urge Questionnaire (AUQ) (Bohn, Krahn et al. 1995) is an 8-item, self-administered state measure assessing the urge for an alcoholic drink at the time the questionnaire is completed and provides an index of acute craving. The AUQ contains four items pertaining to the desire to drink: two items regarding expectations of positive effects from drinking, and two items relating to the inability to avoid drinking if alcohol were present. This measure has strong correlations with measures of alcohol dependence and severity.
- The Clinical Institute Withdrawal Assessment for Alcohol Scale–revised (CIWA-Ar) (Sullivan, Sykora et al. 1989) is a 10-item scale for clinical quantification of the severity of alcohol withdrawal.
- Composite Scale of Morningness (CSM) is a 13-item survey that assesses whether the participant is most alert in the morning or later in the day, e.g. an “owl” or a “lark.” (Smith, Reilly et al. 1989)
- Insomnia Severity Index (ISI) is a five-item questionnaire that assesses the quality of sleep and its effect on activities of daily living. (Bastien, Vallieres et al. 2001)

Study staff will train subjects to use the IVR phone system. Subjects will be instructed on when to call in each day and how to use the phone system to complete the daily assessment. They will receive a written copy of the directions with all of the questions and responses. Study staff will program subjects’ study identification number into the IVR phone system after they have been randomized to study medication.

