Multilevel models similar to those described above will be used to evaluate the associations between alcohol expectancies and daily drinking and how these associations vary as a function of medication group and rs2832407 genotype. Similar to Kranzler et al. (2013), we will focus on predicting nighttime drinking (i.e., drinks consumed after the early evening report), but here we will use alcohol-related expectancies reported during the early evening in the daily survey. Nighttime drinking levels will be determined by subtracting the number of drinks consumed during the current day from the total number of drinks consumed for that day (reported the following day). We will follow the general analysis scheme used by Kranzler, Armeli et al (2013), but will use mixed effects/multilevel models, rather than generalized estimating equations (GEE) models (Walls, Jung et al. 2006, Schafer 2006). We will examine the number of drinks consumed (using a Poisson model). We will use the HGLM module of the HLM7 program, as it is more flexible for some of our models than PROC GLIMMIX in SAS. Analysis will focus on the last six weeks of treatment, consistent with the analyses of the primary outcome in Specific Aim 1.

Predictors in these models will include 6 day-of-the-week contrasts in the level-1 model (i.e., including responses that change over days within person), to control for day of the week trending in the outcomes [e.g., greater propensity to drink on weekends (Armeli, Carney et al. 2000, Armeli, Tennen et al. 2000)], along with linear and quadratic study time contrasts and daytime drinking. The day-level predictor of interest (i.e., expectation of positive effects of drinking) will also be included in the level-1 portion of the model. The outcome expectancy

CONFIDENTIAL

predictor will be person-mean centered (91). The level-2 portion of the model (i.e., measures that do not change over days) will include treatment group, binary factors for rs2832407 genotype (i.e., CC vs. A-carrier) and associated interaction terms. This analysis will test the hypothesis that TOP will significantly reduce positive alcohol expectancies relative to PLA, but only in C-allele homozygotes, similar to the analysis of the primary outcome in Specific Aim 1.

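### Aim 2 has no designated pre-dose report of the daily expectancy and confidence items, and its model adjusts for no baseline value, so its between-person contrasts are less precise than they need be

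*Combined protocol and SAP*

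**What the plan says.** **Timing of the daily reports.** Section 6.3 lists the "Daily Interactive Voice Response (IVR) Telephone Call (daily for 12 weeks, beginning with the initiation of treatment". Section 3.1 agrees: "Daily reports during the treatment period will be obtained using interactive voice response (IVR) to identify subjective correlates of medication effects". Section 3.1 also describes a week before treatment ("Following a one-week pre-treatment assessment period, subjects will receive 12 weeks of treatment") but assigns no daily calls to it. Under section 6.3, staff programme each subject's "study identification number into the IVR phone system after they have been randomized to study medication". The expectancy and confidence items are part of this call. Table 2 gives them no other place, and it marks no IVR report at screening.

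**Hypothesis.** Section 2.2 states that "topiramate treatment will significantly reduce both positive alcohol-outcome expectancies and confidence in resisting heavy drinking across the weeks of the study" in C-allele homozygotes but not in A-allele carriers. Section 7.2 puts it as a comparison with placebo: "This analysis will test the hypothesis that TOP will significantly reduce positive alcohol expectancies relative to PLA, but only in C-allele homozygotes". On the window, section 7.2 says: "Analysis will focus on the last six weeks of treatment, consistent with the analyses of the primary outcome in Specific Aim 1".

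**Model.** In section 7.2 (Aim 2) the outcome is nighttime drinks. Level 1 holds day-of-week and time terms, daytime drinking, and positive expectancy centred on each person's own mean. Level 2 holds treatment, genotype and interaction terms. No baseline value is listed.

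**Pre-treatment data that do exist.** The TLFB at intake covers the previous 90 days (section 6.2). The AUQ is given at Visit 1 (Table 2). It includes two items on expected positive effects of drinking and two on being unable to avoid drinking (section 6.3). All Visit 1 assessments are completed before the first medication is given.

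**The concern.** The hypothesis speaks of a reduction in expectancy and confidence ratings, but no value of the same items is planned from before treatment. People differ in how they habitually answer such items. Part of that difference will persist into weeks 7-12 and add to the error of any between-person contrast on them. The randomisation factors are sex, genotype and past-month heavy drinking days (section 5.3), with site and treatment goal (section 3.1). None of them balances expectancy or confidence. Early treatment weeks cannot stand in for a baseline, because they fall after randomisation and on study drug.

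At stake are the precision of a secondary aim, the ability to adjust for chance imbalance on these items, and any statement about change from pre-dose.

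**Working it through.** The plan gives no precision figure for these contrasts, so there is none to reproduce. Section 7.1 powers Aim 2 for moderation of the within-person link between evening expectancy and nighttime drinking, which is a different quantity.

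**1. What needs a baseline and what does not.**
- Topiramate minus placebo within CC, within A-carriers, and the difference between the two: estimable without bias from on-treatment data, because each genotype stratum is randomised.
- Within-person change from pre-dose on the IVR items: not computable.
- Precision of the between-person contrasts, and adjustment for chance imbalance: improved by a baseline.

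**2. Size of chance imbalance.** With 200 randomised in four groups of comparable size, n is about 200/4 = 50 per cell. In units of the person-level SD, the chance baseline difference has SD:
- between arms within one genotype, sqrt(2/50) = 0.20;
- for the interaction contrast, sqrt(4/50) = 0.28.

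Only the part that persists into weeks 7-12 affects the result.

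**3. Gain from one pre-dose report, with expectancy or confidence as the outcome.**

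Inputs from the documents: 42 days in the last six weeks and about 20% missing (section 7.1), so 42 × 0.8 = 33.6 reports per person.

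Assumptions not in the documents: single-report intraclass correlation (ICC) 0.35 to 0.65; stability of a person's true level from baseline to weeks 7-12 of 0.6 to 0.8.

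Formulas: reliability of a mean of n reports = ICC / (ICC + (1 − ICC)/n); r = stability × sqrt(reliability of baseline × reliability of outcome); variance reduction = r²; standard error reduction = 1 − sqrt(1 − r²).

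| | Low end | High end |
|---|---|---|
| ICC, stability | 0.35, 0.6 | 0.65, 0.8 |
| Reliability of baseline (n = 1) | 0.35 | 0.65 |
| Reliability of outcome (n = 33.6) | 0.948 | 0.984 |
| r | 0.6 × sqrt(0.35 × 0.948) = 0.35 | 0.8 × sqrt(0.65 × 0.984) = 0.64 |
| Variance reduction | 12% | 41% |
| Standard error reduction | 6% | 23% |

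**4. Cross-check with another model.** Take one pre-treatment weekly value, the mean of m = 6 weekly values as outcome, and equal correlation rho between all weeks. Then r² = rho² / ((1 + (m − 1)rho)/m). Section 7.1 assumes 0.35 for the weekly Aim 1 outcome. Borrowing it here gives 0.1225/0.4583 = 0.267, so the adjusted variance is 73% of the unadjusted. Over rho from 0.2 to 0.7 it runs from 88% to 35%. The direction and order of size agree.

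**5. Dilution.** If only a fraction f of subjects has the report and the rest carry a missing-baseline indicator, the pooled residual variance is f(1 − r²) + (1 − f) = 1 − f·r². With f = 0.5, purely as an illustration, the cut is 0.5 × 12% to 0.5 × 41%, or about 6% to 20%.

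**The case against.** **Validity.** A reader might infer that Aim 2 is biased, or that a reduction cannot be shown in either genotype. The documents do not support that. Section 7.2 defines the effect relative to placebo, and randomisation is stratified by genotype, so the contrast is valid in each stratum without a baseline. Section 2.2 refers to the weeks of the study, which the daily reports cover. Neither section explicitly asks for change from pre-dose.

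**Existing data.** A reader might also infer that nothing is available to adjust for. Drinking has a 90-day record and the AUQ touches both constructs. Section 7.2 (Aim 1) lets covariates be added for imbalance, and it calls the Aim 2 models similar. This largely stands, with limits: the TLFB does not separate nighttime drinking, the AUQ is a different instrument measuring momentary urge, and permission to add covariates does not name them in advance.

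**Relevance of the figures.** It is tempting to apply the 12% to 41% to the Aim 2 model as written. It does not apply there. Expectancy enters that model as a person-mean-centred predictor, so between-person expectancy levels are removed from it, and a baseline report would do little for the powered within-person slope. This objection stands in full.

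**First call.** Week 1 has only an evening dose (Table 1) and calls are made at 5-8 PM, so the first call may precede the first capsule. The plan neither fixes that order nor labels the call a baseline.

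**Practicality.** This is Version 18. The documents do not say how many subjects remain to be enrolled, and a clinic training call may differ from a home evening report. Both limit the benefit of new collection but leave the free covariate change untouched.

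**Conclusion.** The point holds as a modest, correctable weakness in a secondary aim. No pre-treatment report of the IVR expectancy and confidence items is designated, and no baseline value is named in the Aim 2 model. The comparison with placebo is unbiased, and no power shortfall has been shown. What is lost is within-person change from pre-dose on these items and some precision in the between-person contrasts.

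For models with expectancy or confidence as the outcome, one pre-dose report would cut the person-level variance by about 12% to 41% (standard error by 6% to 23%) among subjects who have it. The range rests entirely on the assumed ICC and stability. No figure is offered for the TLFB or AUQ covariates, since the documents give no correlation between them and the Aim 2 outcomes.

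**What to change.** 1. **Section 7.2 (Aim 2).** Enter baseline TLFB drinking as a level-2 covariate in the nighttime drinking model. Enter the baseline AUQ as a level-2 covariate in any model with expectancy or confidence as the outcome. Both are already scheduled for all subjects, so the cost is wording only.

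2. **Section 6.3 and Table 2, for subjects still to be enrolled.** Have the Visit 1 IVR training call completed before the first dose, designate it as the baseline report, and use it as a level-2 covariate with a missing-baseline indicator for earlier subjects. If setting up the IVR identifier after randomisation gets in the way, the paper diary already provided for in section 6.6 can be used. The cost is one call of under 5 minutes per subject at a visit where IVR training already takes place.

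3. **Sections 2.2 and 7.2.** Word the expectancy and confidence hypothesis as a between-arm difference during treatment, by genotype. This costs wording only and keeps the estimand that section 7.2 already states.

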6.4 Visits 2-8 (Weeks 2-11; Treatment Visits)

At each visit, the study nurse will dispense study medications as shown in Table 1. In the event that scheduled visits change or the subject's dosage is adjusted by the study physician, medication will be mailed via a UPS or Fedex to the subject, to ensure that they have enough medication to get them to their next scheduled visit. The study physician will approve all medication mailed to subjects and the study nurse or physician will document the medication dispensed via mail and call to instruct the subject on how the medication should be taken and to document all AEs. Study staff will also document whether the mailed medication was received by the subject.

The dosage of medication will be increased only as tolerated and subjects experiencing intolerable adverse effects will have their dosage decreased gradually to the highest tolerated dosage, which will be determined by the study physician. Upward titration following a dose reduction will be allowed during the trial to minimize adverse effects while maximizing potential efficacy. Dose titration will be carefully documented in the study chart along with the clinical rationale. The study nurse, in consultation with the study physician, will provide guidance for subjects as they increase their medication dosage, per the titration schedule. Subjects will be given study medication consisting of topiramate or matching placebo and titrated up to a maximum of 200 mg/day of topiramate or the placebo equivalent (see Table 1).

During the 12-week treatment period, subjects will return to the clinic weekly (+/- 4 days) for the first 6 weeks and every other week (+/- 4 days) for weeks 7-12. At each visit, the subject's BrAC, weight, and vital signs will be measured. Subjects will be asked not to drink before coming to the scheduled visits. Subjects will be asked to complete a breathalyzer test. If a subject's breath alcohol concentration is $\geq 0.02\%$, an investigator will evaluate whether the subject is too impaired to complete the study assessments. The study visit may be completed at the discretion of the investigator. If the subject is deemed to be unable to complete assessments, the investigator may ask the subject to wait until his or her blood alcohol level decreases or if that is not feasible to return the next day after having consumed no alcohol. Prior to discharge from the TRC, a clinician will assess the subject to ensure that it is safe for the subject to leave. Study staff will complete the following assessments with all subjects (the exception being that only for women of childbearing potential, will study staff obtain a urine sample for a pregnancy test).

Subjects who are deemed suitable for assessment will complete questionnaires and be interviewed by the study nurse about their concomitant medications, adverse events, and protocol compliance. At every treatment visit (i.e., for a total of 10 sessions), the study nurse will deliver the MM intervention. Study staff will also administer the following assessments, as described above:

- *The Timeline Follow-back (TLFB)*: To collect data on daily drinking, cigarette use, and medication taken.
- *The Patient Health Questionnaire (PHQ-9)*: To measure depressive symptoms.
- *The International Neuropsychiatric Interview 6.0 (Mini 6)*: Suicidal risk will be assessed using the MINI Suicidality section (B) at each study visit and, if rated greater or equal to 9 (i.e., clinically significant suicidal ideation), the physician will be consulted to decide on the appropriate clinical management.

CONFIDENTIAL

- *The Clinical Institute Withdrawal Assessment for Alcohol Scale–revised (CIWA-Ar)* (Sullivan, Sykora et al. 1989) is a 10-item scale for clinical quantification of the severity of alcohol withdrawal.
- *Medication Adverse Effects Checklist*
- *Measures of treatment received*
- *Daily Interactive Voice Response Telephone Call (daily for 12 weeks, beginning with the initiation of treatment)*
- *ISI*

Also, at the **week six visit**, the study staff will obtain a blood sample to measure bicarbonate levels, as topiramate can cause metabolic acidosis, and GGTP and %dCDT concentrations to corroborate self-reported alcohol consumption. At visits 5 (week 5) and 7 (week 8), study staff will obtain a urine sample for a pregnancy test for subjects who are women of childbearing potential. If a subject reports being pregnant or tests positive, she will immediately be withdrawn from treatment with study medication, referred for obstetric evaluation, and advised to discontinue all drinking.

